## 1) Protocol Title

Computer Assisted Family Intervention to Treat Self-Harm Disparities in Latinas and Sexual/Gender Minority Youth (CA CIFFTA)

# 2) IRB Review History\*

IRB for NIH "Just in Time" was approved on 9/1/2017.

# 3) Objectives\*

The study described in the protocol is a randomized trial at UM. The study will enroll 100 11-18 year old youth with a self-reported act of self-harm in the past 6 months and their families. This study is designed to refine and test the efficacy of a computer assisted culturally informed and flexible/adaptive intervention for Latino adolescents for whom self-harm behaviors are a health disparity—specifically, Latinas and sexual/gender minority youth. The specific aims of this study are:

- To build on the Computer Assisted CIFFTA intervention by creating a web-site and web-based delivery system and by adding content that is relevant for the factors that maintain self-harm in Latina adolescents (e.g., depression, family conflict, substance use, and emotion dysregulation) and for unique stressors often linked to sexual/gender minority youth and those exposed to trauma.
- 2) To investigate the preliminary efficacy of the Computer Assisted CIFFTA in reducing self-harm and in modifying the factors that place youth at risk for self-harm (e.g., depression, family conflict, substance use, and emotion dysregulation) when compared to controls (Treatment-As-Usual).
- 3) To investigate the linkages between co-existing problem areas (e.g., selfharm, risky sexual behavior, substance use) to see if there is evidence of a syndemic.
- 4) To investigate the relationship of culture-related variables (e.g., acculturation, familism, and Hispanic Stress) to the key factors hypothesized to contribute to self-harm behavior (i.e., depression, family conflict, substance use, and emotion dysregulation).

# 4) Background\*

### **Significance and Rationale**

Suicide is the second leading cause of death in youth ages 10-24, and self-harm which includes nonfatal suicide attempts (SA) and non-suicidal self-injury (NSSI)—is prevalent and is a risk factor for future suicide attempts and suicide completion. Selfharm does not typically emerge in a vacuum; it is commonly found to occur with other mental health (e.g., depression and emotion dysregulation) and behavioral (e.g., alcohol and drug use, risky sexual behavior, and externalizing behavior) symptoms. Evidence suggests that these behaviors occur in clusters as described by Syndemic theory and, if untreated, lead to severe adverse substance abuse, violence, and HIV/AIDS (SAVA) disparities in youth and other vulnerable populations. A cross-sectional investigation of high school youth found that engagement in risky sex, self-harm/cutting, and externalizing behaviors tended to co-occur among youth who reported using illicit substances. In a study with adolescents participating in an intensive psychiatric treatment program, risky sexual behaviors, including inconsistent condom use, were found to be associated with self-harm behaviors. In the treatment of these youth, research has suggested that (a) several stressors are likely to arise with non-suicidal self-injury and suicide-related injuries and (b) any program seeking to treat existing risk factors and prevent repeated self-injury and suicide should be prepared to address these stressors. Among these stressors are the marginalization experienced by sexual and gender minority youth, traumatic experiences, chronic family conflict, and alcohol use. In addition, culture-related variables may place Latinas at even higher risk due to breakdowns in family protective factors.

### Hispanic/Latino adolescents, self-harm, mental health, and risky sexual behaviors

A set of health disparities often linked together in Hispanic/Latino youth are selfharm behaviors, rates of depressive symptoms, and HIV rates. According to the 2015 Youth Risk Behavior Surveillance System (YRBSS) survey of high school students, Hispanic youth reported feeling sad or hopeless at higher rates than non-Hispanic White youth, 35.3% versus 28.6%. Among all high school students who completed the survey, 17.7% of youth reported having seriously considered attempting suicide in the previous vear and Hispanic rates were higher than non-Hispanic youth. Hispanic/Latino females appear to be at particularly high risk-reporting the highest prevalence of having felt sad or hopeless (46.7%), of having seriously considered attempting suicide (25.6%), of having made a suicide plan (20.7%), and of having attempted suicide (15%) in the past 12 months. Another health disparity area also found in Hispanic/Latino females- and possibly linked to self-harm and depression profiles-involves risky sexual behavior and HIV risk. Hispanic/Latino youth have an earlier age of onset for sexual intercourse than non-Hispanic White youth and are less likely to use condoms consistently, which may place them at increased risk for pregnancy, STIs, and HIV. According to the 2015 YRBSS, the high school prevalence of having ever had sexual intercourse was highest among Hispanic/Latino females at 39.8%. In 2014, Hispanic teen birth rates were more than two times higher than the rate for non-Hispanic White teens. In 2013, of new diagnoses in the United States among youth 24 and younger 20% were Hispanic/Latino youth compared to 17% of non-Hispanic White youth. Among male adolescents ages 13-24 living with a diagnosis of HIV infection at the end of 2012 in the US, 20% were Hispanic/Latino compared to 15% non-Hispanic White. Of the new infections in 2015, Hispanic/Latino gay and bisexual adolescent males were infected at the second highest rate. Among females in the age group who were diagnosed, 18% were Hispanic/Latina compared to 13% non-Hispanic White female adolescents.

There are individual, familial, acculturation and immigration-related factors, and trauma-related factors that have been hypothesized to contribute to this self-harm disparity in Latinas. Zayas (2011) postulates that this set of factors can have a debilitating effect on mental health, negatively impacting an individual's ability to cope and increasing the risk for self-harm behaviors. Traumatic immigration experiences and prolonged immigration-related separation between caregivers and youth can also cause

high stress and family disruptions resulting in increased risk for self-harm behaviors. A recent study of Hispanic/Latino youth found that the female adolescents with exposure to a traumatic event and who reported low family cohesion reported more symptoms of anxiety and depression. These findings are consistent with literature pointing to the negative effects of poor family cohesion on symptoms of depression and highlights the importance of identifying and addressing these experiences in treatment to avoid worsening symptom and self-harm. Hispanic/Latino youth may experience family conflict and a loss of family cohesion as they acculturate to the US culture. Studies have suggested that Hispanic/Latino girls and boys have different acculturation experiences and that Hispanic/Latino girls may acculturate faster than boys when they are attracted to less traditional gender roles in the United States. Due to gender role expectations in Hispanic/Latino families, adolescent females report greater responsibilities at home, less freedom to socialize outside of the home, and greater supervision than males. Research has also suggested that females place more importance on interpersonal connections and closeness than males and that Hispanic/Latino females are more negatively affected by family conflict than their male counterparts. Thus, girls may experience more family conflict and less family cohesion when parents and other relatives impose rules on them and when they rebel against these gendered restrictions. As a result of the family disruptions, parenting quality and other protective family factors can decline and the adolescent girl may be exposed to high levels of negative emotion from parents or other family members. These factors may negatively impact her ability to cope and regulate emotions, and impact internalizing and externalizing behaviors leading to self-harm behaviors.

### LGBT and Sexual and Gender Minority Youth and Self-Harm

Lesbian, gay, bisexual and transgender youth are a minority group that are at increased risk for self-harm. In the year preceding the YRBSS 2015 survey, 60.4% of gay, lesbian, and bisexual students reported feeling so sad or helpless that they stopped doing some usual activities, 42.8% had seriously considered attempting suicide, and 29.4% had attempted suicide one or more times. LGBT youth are at increased risk of negative health outcomes such as increased rates of STIs/HIV, increased use of alcohol and drugs, and issues related to weight. LGBT youth engage in high risk sexual behaviors such as early age of first sexual intercourse, more lifetime and recent sex partners, and drinking alcohol or being high during last sexual intercourse, and are less likely to use a condom during intercourse than heterosexual peers. They are also five times more likely to use alcohol and drugs than their heterosexual peers. Meta-analyses show that adolescents and young adult MSM show high rates of several serious symptoms including substance use, risky sexual behaviors that can lead to HIV, and self-harm behaviors. Further, these researchers hypothesize that the strong linkages between the rates of these behaviors point to a possible syndemic in which contextual conditions (e.g., marginalization and victimization) may significantly contribute to the co-occurrence of these symptoms.

Minority Stress Theory suggests that sexual minorities experience unique, recurring stressors that lead to unhealthy behaviors. LGBT youth experience homelessness at a higher rate than their non-LGBT counterparts and experience stressors such as discrimination, rejection, violence, abuse, lack of support, and trauma. Previous research has linked PTSD symptoms and self-harm behaviors. A 2016 CDC report comparing LGB youth to heterosexual youth in high school showed that LGB youth were more likely to be physically forced to have sex (18% LGB vs. 5% heterosexual), to experience sexual dating violence (23% LGB vs. 9% heterosexual), to experience physical dating violence (18% LGB vs. 8% heterosexual), and to be bullied at school or online (at school: 34% LGB vs. 19% heterosexual; online: 28% LGB vs. 14% heterosexual). LGB students were more likely to miss school in the recent past due to feeling unsafe at school. In combination or individually, these risk factors greatly increase the risk for self-harm and/or suicide in LGBT youth. Parental rejection following their child's disclosure has also been associated with various negative outcomes, including depression, substance abuse, academic and conduct problems, and troubled interpersonal relationships.

Hispanic/Latino LGBT youth possess unique cultural factors that place them at additional risk for self-harm behaviors and being both an ethnic minority and a sexual minority results in a compounding of adverse outcomes. A large national study showed that compared with White LGBT youth, Latino LGBT youth were more likely to attempt suicide. Latina LGBT youth had significantly higher rates of suicide attempts in the previous year than any other racial/ethnic group in the study. Latino LGBT boys reported twice the amount of feeling sad in the last year than boys of other racial categories. Fewer than half of LGBT Latino youth have an adult in their family they can turn to if worried or sad, compared to 80% of their non-LGBT Latino peers; and among LGBT youth ages 13-17 who disclosed to their parents, about one-third lacked family acceptance.

Additionally, LGBT Latino youth are more likely to face harassment and violence in the community than their non-LGBT Latino peers. Results of an online survey of approximately 2,000 LGBT Hispanic youth suggest that they may experience differences in the process of coming out, parental and family support, and the extent to which they feel a sense of belonging in their community when compared to non-Hispanic White LGBT youth. Hispanics are among the most religiously observant populations in the country and while faith can be a protective factor, it can conflict with an LGBT identity. **Issues in the treatment of self-harm risk and its underlying conditions** 

Research investigating ways to reduce the risk of future self-harm behavior and co-occurring behaviors (e.g., HIV and STIs) should consider factors that help to maintain these conditions and that can be modified through treatment. The literature suggests that depression, emotion dysregulation, family conflict, and substance use can each create the conditions that increase risk for repeated acts of self-harm. For example, studies support the link between non-suicidal self-injury and emotion dysregulation such that engagement in NSSI results in negative affect reduction and emotion regulation. When adolescents report more than one of these conditions, they may be at particular risk for self-harm. Treatment of these conditions can substantially change the course of the syndemic and development long term.

Family based interventions have been among the most efficacious treatments across a wide variety of adolescent disorders including ADHD, Depression, and Disruptive Behaviors and have been recommended for use with the LGBT population. Family interventions are also the preferred mode of treatment for ethnic minority adolescents. The utilization of a treatment that works well for Hispanics is important given the evidence that Hispanics receive less treatment, poorer quality treatment, and treatment that is not culturally competent. Statistics show that Hispanics utilize mental health services at half the rate of non-Hispanic Whites despite reporting more mentally unhealthy days.

Despite the efficacy of family-based interventions, there have also been major implementation challenges that require continued treatment innovation. One set of implementation challenges includes: sustainability of a multicomponent treatment that requires considerable staff time to deliver, difficulties related to scheduling and reaching underserved populations, and transportations. The logistics of frequent office visits may be one of the problems contributing to the underutilization of services by minority adolescents and families. The significance of the proposed Research Project is that it has the potential to deliver services effectively and efficiently-because some of the key interventions are packaged and delivered through a web-based platform that is easy to use, requiring fewer office based visits, and allowing families to access resources at times that are more convenient to families with multiple jobs. The technology can be made more attractive to adolescents, relevant to their concerns, and consistent with their lifestyles. Interventions with prominent technology components may keep adolescents continually engaged in therapeutic activities that would otherwise be confined to scheduled sessions. The benefits of technology are described further in the Innovation section below.

A second set of challenges is the difficulty in creating a "one-size-fits-all" treatment. Adolescents and families display great diversity in terms of cultural background, life stressors, strengths and needs, and clinical symptoms. In the proposed treatment, we aim to reduce the risk of repeated incidents of self-harm and suicide related behavior and we understand that to accomplish this goal, our treatment must have interventions that focus on those factors that we hypothesize to maintain the risk. In other words, our treatment must seek to decrease depression, emotion dysregulation, family conflict, and substance use. In order to increase the ecological validity of the treatment sessions, the manualized intervention must also be designed to address the day to day stressors that emerge in the lives of Latina and LGBT youth and that contribute to depression, emotion dysregulation, family conflict and substance use. Content that includes discussion of marginalization, traumatic events, culture-related factors at the individual and family levels must all be clearly articulated in the treatment manual if it is to have a high degree of ecological validity. A major challenge for many manual-guided interventions is that they must adapt considerably to address these unique culture-related (e.g., facing stressors due to acculturation, immigration, discrimination due to race, ethnicity), unique life stressors (e.g., rejection due to being LGBTQ, exposure to trauma, discrimination and rejection), and clinical profiles (e.g., family risk factors, co-occurring psychiatric disorders). When manualized interventions do not clearly articulate the treatment adjustments needed to address these complexities, clinicians are required to make adjustments in an idiosyncratic fashion. These adjustments become challenges to fidelity and become more difficult to replicate. A second area of significance of the proposed work is that it will utilize a culturally informed intervention delivered in an adaptive framework that includes modular material that can be selected to address many of these commonly found stressors (e.g., emotion dysregulation, minority and acculturation stress) and the explicit decision rules that facilitate replication. In the Innovation section below, we describe the adaptive framework of the Culturally Informed and Flexible Family-Based Treatment for Adolescents (CIFFTA).

The proposed study: (a) enhances the content of the original Computer Assisted Culturally Informed and Flexible Family-Based Treatment for Adolescents (CA CIFFTA) to directly address the new key targets (e.g., depression, emotion dysregulation, LGBT and trauma-related stressors), (b) refines the technological aspects of CA CIFFTA for web-based delivery and use feedback and data from our first small trial, and (c) tests the preliminary efficacy of the new intervention and its delivery system in a randomized trial of 100 adolescents and their parents. We seek to reduce risk for repeated self-harm and risky sexual behavior by showing treatment effects on depression, emotion regulation, substance use, and family functioning. With the large numbers of adolescents that go without services due to service utilization obstacles and stigma, technologyrelated innovations that can enhance treatment effects and/or reduce barriers should be considered an urgent need.

## 5) Inclusion and Exclusion Criteria\*

Inclusion Criteria: To be included in the study, the adolescent must: (a) be 11 to 18 years old; (b) self-report an act of self-harm in the past 6 months, (c) meet cut-off criteria on two of the four maintaining factors (depression, emotion dysregulation, family conflict, substance use), and (d) live with at least one parent-figure who agrees to participate in assessments and treatment. Participants should be willing and able to participate fully in the protocol (e.g., to accept assignment to either condition, to provide sufficient locator information for follow-up, to allow their treatment sessions to be recorded for fidelity/process assessment and supervision). All family members in the household are invited to participate in treatment. Our success at engaging family members is evident in that an average of three family members per household participated in family intervention studies.

Exclusion Criteria: Exclusion criteria include: (a) history of DSM V Developmental Disorders, Elective Mutism, Organic Mental Disorders, Schizophrenia, Delusional Disorder, Psychotic Disorder, and Bipolar Affective Disorder. We will exclude youth who are actively in crisis and reporting current ideation with a specific plan and with means to complete the plan. If a youth is referred in this state, it will be a priority to utilize a warm-handoff procedure to connect them to a more intensive treatment program.

Eligibility Screening: Staff at the referral sites will be trained to identify youth appropriate, namely a self-harm event, for the study. When a youth/family is identified as potentially appropriate the referral site will ask the family to sign a release of information so that study personnel can contact them to schedule a formal screening. If the form is signed, the referral site will contact the designated study personnel (assessor) and provide the contact information for the family. The study personnel will contact the family and schedule an appointment to conduct the screening. When the family attends the appointment, the screening measures (Self-harm, family conflict, emotion dysregulation, depression and substance abuse) will be administered to determine eligibility. (see sections below)

## 6) Number of Subjects\*

A total of 100 11-18 year-olds with a self-reported act of self-harm in the past 6 months and their families will be involved in the proposed study.

## 7) Study-Wide Recruitment Methods\*

NA. This is not a multicenter study. Subjects will be recruited by methods under the control of the local site. See recruitment procedures in section 24) Recruitment Methods.

## 8) Study Timelines\*

Both conditions will be tested as 16-week interventions. There will be an additional 8-week period of continuing care, then 6 months of no contact, followed by a final assessment. The final assessment will occur 12 months after baseline. The duration of an individual subject's participation in the study will be 1 year (including all follow-up assessments).

The duration anticipated to enroll all study subjects is 35 months. Recruitment will begin in month 8 of the study and end in month 43.

The estimated date for the investigators to complete this study (including primary analyses) is 60 months.

## 9) Study Endpoints\*

- 1. Primary
  - a. Self-harm
- 2. Secondary:
  - a. Depression
  - b. Family functioning
  - c. Alcohol/substance use
  - d. Emotional dysregulation
  - e. Risky sexual behaviors

There are no safety endpoints in this study.

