NCT03709472

Computer Assisted Family Intervention to Treat Self-Harm Disparities in Latinas and Sexual/Gender Minority Youth

Statistical Analysis Plan 8/21/24

Data were analyzed using SPSS Version 29 (IBM, 2023). We began our analyses by documenting the number of session and hours of treatment to assess CIFFTA's feasibility and acceptability. We conducted logistic regressions to examine whether baseline characteristics predicted those participants who successfully reached termination and T2 assessments. To examine whether changes in adolescent symptoms of depression over time differed by treatment, a mixed ANOVA was used with depression scores as the within-subjects variable and treatment condition as the between-subjects variable. We used the same analytic strategy to determine whether changes in emotion regulation and family connectedness differed over time by treatment. A series of mixed ANOVAs were used with the Total scores from the PHQ-9, the Difficulty with Emotion Regulation Scale and the Family Connectedness Scale as the within-subjects variables and treatment condition as the between-subjects variable. When effect sizes are reported, cutoffs for partial eta-squared effect sizes are small .01, moderate .06, large .14. Additionally, Chi-Square Tests of Association were used to determine whether the proportion of youth endorsing whether they could talk to their parent about problems differed over time. This analysis was conducted by condition examining mothers and fathers separately.

A complementary analytic strategy was used to investigate change in youth who entered the study with presenting problems in the clinical range at baseline assessments based on established clinical cutoffs (i e., those with at least mild levels of depression at baseline). Descriptive statistics were used to determine the rates of suicidal thoughts and self-harm at baseline and termination by condition. In addition, Chi-Square Tests of Association were used to determine whether the proportion of youth endorsing thoughts of suicide differed by treatment condition.

We also used the Reliable Change Index (RCI) to determine whether the magnitude of change was statistically reliable rather than due to random fluctuations caused by measurement error (Jacobson & Traux, 1991). We examined symptoms of depression.

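### Two of the five secondary endpoints, alcohol/substance use and risky sexual behavior, have no analysis in the SAP

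*Protocol*

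**What the plan says.** Protocol section 9 names self-harm as primary and five secondary endpoints: depression, family functioning, "Alcohol/substance use", emotional dysregulation and "Risky sexual behaviors".

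Substance use is built into the design. Aim 2 (section 3) gives it as an example of a risk factor to be modified relative to treatment as usual. Section 5 makes it one of the four maintaining factors used for eligibility. The closing paragraph of section 4 says risk will be reduced by "showing treatment effects on depression, emotion regulation, substance use, and family functioning". The same sentence makes risky sexual behavior a target of the treatment, and Aim 3 names both domains.

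Both are to be measured. The Measures paragraph of section 10 lists substance use as an immediate outcome, and the Phase I text of section 10 places risky sexual behavior in the REDCap battery.

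The SAP's between-arm analyses start with depression: "To examine whether changes in adolescent symptoms of depression over time differed by treatment, a mixed ANOVA was used". The same method is then used "to determine whether changes in emotion regulation and family connectedness differed over time by treatment". The scales are given as "Total scores from the PHQ-9, the Difficulty with Emotion Regulation Scale and the Family Connectedness Scale". The rest of the SAP covers completion of T2, talking to parents, a clinical-range analysis, suicidal thoughts and self-harm, reliable change in depression, and logistic models of plausible mechanisms.

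**The concern.** A protocol that lists an endpoint commits the trial to reporting it. If the SAP is followed exactly, a reader of the results would learn nothing about the effect on substance use or risky sexual behavior, although both were to be collected. Aim 2 would be answered for depression, emotion regulation and family functioning, and left open for substance use.

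The timing adds to the problem. The SAP is dated 8/21/24 and describes analyses as already done. It gives no reason for leaving the two endpoints out, so the documents cannot show whether the choice was made before or after the data were seen. Meanwhile an outcome that section 9 does not list, thoughts of suicide, receives a between-arm test. Dropping listed outcomes and testing an unlisted one is the pattern that pre-specification is meant to exclude, whatever the reason for it here.

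**Working it through.** The documents state no figure to reproduce on this point, so the check sets the section 9 list against every analysis in the SAP.

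**1. Secondary endpoints against SAP analyses**

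| Section 9 secondary endpoint | Analysis in the SAP |
|---|---|
| Depression | Mixed ANOVA on PHQ-9; clinical-range analysis; reliable change |
| Family functioning | Mixed ANOVA on family connectedness; talking to mother or father |
| Alcohol/substance use | None |
| Emotional dysregulation | Mixed ANOVA on the emotion regulation scale |
| Risky sexual behaviors | None |

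Listed: 5. With an analysis: 3. Without: 5 − 3 = 2, and 2/5 = 40%. The count accepts family connectedness as a measure of family functioning.

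**2. Maintaining factors against the mechanism models**

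Section 5 gives four factors: depression, emotion dysregulation, family conflict and substance use. The last paragraph of the SAP enters depression, emotion regulation, and two family measures (parent communication and connectedness). Three of the four are represented and 1/4 is not: substance use.

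**3. Could another part of the plan cover the gap?**

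- The clinical-range analysis might have taken in substance use, but the SAP defines it as "those with at least mild levels of depression at baseline".
- The logistic regressions of T2 completion use unnamed baseline characteristics. Baseline substance use could be one of them, but predicting retention is not an endpoint analysis.
- The protocol text supplied has no statistical section. Section 12 says only that the study statistician will analyze the data.

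**4. Outcomes tested but not listed**

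Section 4 describes self-harm as including nonfatal suicide attempts and non-suicidal self-injury. Thoughts of suicide are neither of these, and they are not a secondary endpoint, yet the SAP compares them by treatment condition. Talking to parents is different: it fits family functioning, and its chi-square test looks at change over time within each condition. The clear count of unlisted outcomes tested between arms is therefore one.

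**5. Can a model for the omitted endpoints be supported?**

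The documents give no event rate, so these are assumptions: 70 to 100 youth analysed (100 planned; about 70% of adolescent assessments obtained at 16 months in the team's previous trial, section 10) and 10% to 40% with the event.

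- Events: 70 × 0.10 = 7, up to 100 × 0.40 = 40.
- Arm, baseline value and four stratification factors need at least 1 + 1 + 4 = 6 parameters: 7/6 ≈ 1.2 to 40/6 ≈ 6.7 events per parameter.
- Arm and baseline value alone need 2 parameters: 7/2 = 3.5 to 40/2 = 20 events per parameter.

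The fully adjusted model is fragile across the whole range. The two-parameter model is workable except at the low end.

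**The case against.** The best defence is that this is a trial of preliminary efficacy, that the endpoints are secondary, and that the SAP need not be the trial's last word. It works with two time points although the protocol also schedules T3 at 12 months, so it plainly does not cover everything collected. This has force on one point. A reader might infer that the two endpoints will never be reported or that results are being withheld. The documents show only that no analysis is specified. Nor does the modest scale of the trial justify dropping listed endpoints without comment, because an estimate with its interval is what a preliminary trial can offer.

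Other tempting readings also go too far:

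- That outcome-reporting bias has occurred. No results are visible, and its size cannot be computed.
- That two unlisted outcomes were tested in place of the two missing ones. Talking to parents is reasonably part of family functioning and is not tested between arms, and nothing shows substitution.
- That the endpoints may not have been measured. The protocol plans to measure both.
- That both omissions fall under Aim 2. Its wording names substance use but not risky sexual behavior, which rests on section 9, section 4 and Aim 3.

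It is also fair to object that a model with all the stratification factors could be unstable. That stands, and the fix allows for it.

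**Conclusion.** The point holds as an omission. Two of five secondary endpoints (40%) have no analysis in the SAP, and one of the four maintaining factors is absent from the mechanism models. At least one outcome outside section 9, thoughts of suicide, is tested between arms. The date and tense of the SAP leave a risk of selective reporting that the documents can neither confirm nor exclude.

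The conclusion assumes that the SAP supplied is the complete plan and that both domains were collected as the protocol intends. The change should be made, but it concerns secondary endpoints only and does not bear on the primary one.

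**What to change.** - For each omitted endpoint, add a between-arm analysis at T2 from the measure already in the battery. Name the instrument, the recall window and the form of the outcome. A logistic model suits any use or any risky sex, and a negative binomial model suits counts.
- Put arm and baseline value in the model. Add stratification factors (gender, type of self-harm, trauma exposure, LGBT status) only as far as the number of events allows. If events are sparse, give rates by arm with a 95% CI for the difference.
- Report the estimate and 95% CI whatever the result, and label both analyses as added after the 8/21/24 SAP.
- Add substance use to the mechanism models.
- Label thoughts of suicide as an additional outcome not listed in section 9.

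The cost is two more secondary estimates and one more mechanism term, from data the protocol already plans to collect. With at most 100 youth the intervals may be wide, and the late addition means that the results should be read as post hoc.
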